#### 11.6.2 Safety Data

Summaries and analysis of safety data will be presented for the Safety Analysis Population. All summaries and analyses will be presented for all participants.

Solicited AEs will be summarized by severity after each study vaccination (through 7 days post study vaccination, Days 1 through 8 and Days 15 through 22) and as the maximum severity over all days. Additionally, solicited AEs will be analyzed by taking the most severe response over the follow-up period, dichotomizing into a binary variable (none versus mild, moderate, or severe) and using standard techniques, such as exact confidence intervals, to summarize the proportion of subjects reporting each symptom, any injection site symptom, and any systemic symptom. Summaries of solicited AEs will be presented for each study vaccination by treatment arm. The proportion of participants reporting symptoms may be compared between treatment arms using Chi-square or Fisher's exact test.

Unsolicited AEs will be coded by Medical Dictionary for Regulatory Activities (MedDRA®) for preferred term and system organ class (SOC). The numbers of SAEs, MAAEs, and AESIs

(PIMMCs) are likely to be small in this trial and will be reported by detailed listings showing the event description, MedDRA® preferred term and SOC, relevant dates (study vaccinations and AEs), severity, relatedness, and outcome for each event. Non-serious unsolicited AEs will be summarized as number and percentage of participants reporting at least one event in each MedDRA® preferred term and SOC, cross tabulated by severity and relationship to study product. Additionally, the proportion of participants and exact 95% confidence intervals of AEs in aggregate and by MedDRA® categories will be computed.

Clinical laboratory data will be summarized by severity for each visit and as the maximum over all post-study vaccination visits. Graphical presentations may include box plots.

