# 2.1. Purpose of the Analyses

The proposed trial will assess, in healthy adults, the safety, reactogenicity, and immunogenicity of the thermostable lyophilized formulation of AV7909 compared to the liquid formation of AV7909.

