# 4. INVESTIGATIONAL PLAN

# 4.1. Overall Study Design and Plan

DMID Protocol 17-0093 is a phase I randomized, parallel-group, double-blind controlled interventional trial in which the safety, tolerability, and immunogenicity of 2 formulations of adjuvanted anthrax vaccine (AV7909), lyophilized and liquid, both manufactured by Emergent BioSolutions, will be assessed and compared. AV7909 is an investigational vaccine that combines the currently licensed Anthrax Vaccine Adsorbed (AVA, BioThrax) with the adjuvant CPG 7909, an oligonucleotide.

Forty healthy young adults, 18 to 45 years old, inclusive, who meet all eligibility criteria, will be randomly allocated to one of two study groups in a 1:1 ratio: 20 will receive AV7909 as the thermostable lyophilized product and 20 will receive AV7909 as the liquid product. Stratification by age category and by sex will assure that near equal numbers of younger (18-30 years) and older (31-45 years) males and females will be assigned to each vaccine. The vaccines will be given intramuscularly in a 2-dose schedule, 2 weeks apart.

Safety will be assessed by evaluation of non-serious unsolicited Adverse Events, Serious Adverse Events (SAEs), Medically Attended Adverse Events (MAAEs), Adverse Events of Special Interest (AESIs) [the AESIs collected in this study are Potentially Immune-Mediated Medical Conditions (PIMMCs)], and by laboratory evaluations. SAEs, MAAEs, and AESIs will be collected from the time of study vaccination through approximately Day 380. Non-serious unsolicited AEs will be collected from Day 1 to Day 64, inclusive. Clinical laboratory evaluations for eligibility will be the following: specific hematology parameters, chemistry parameters, specific urine tests for drugs of abuse, and hemoglobin A1C. Also, an electrocardiogram will be performed at screening and reviewed by an investigator and cardiologist. The cardiologist will determine if any findings on the electrocardiogram are significant and thereby exclusionary. At approximately Day 29, laboratory tests for hematology and chemistries will be repeated.

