# 5. SAMPLE SIZE CONSIDERATIONS

This study is planned to enroll a total of 40 subjects, with 20 subjects in each study arm. This phase I study is not designed to test a formal null hypothesis. Rather, it is intended to obtain sufficient data to obtain meaningful estimates of the immune response induced by either vaccine formulation and to uncover any safety issues that occur at a sufficiently high rate that they might be observed in a study of this size. As such, the type one error rate, alpha = 0.05, is not adjusted for multiple comparisons. While this study is not designed to test any specific null hypothesis, the following tables illustrate the precision and power that is available for select estimates and comparisons of interest.

Table 2 indicates the probability of observing one or more safety events, such as solicited injection site or systemic reactogenicity events or an unsolicited AE of a particular type, for a single treatment arm (N=20), and for all enrolled subjects (N=40).

Binomial confidence intervals (CI) are widest (have the least precision) when the response rate is 50%. Table 3 is presented to indicate the worst-case scenario for precision of observed exact (Clopper-Pearson) binomial confidence intervals.

For each of the primary immunogenicity objectives, a power analysis is provided below for testing the following hypotheses with the planned sample size, where  $p_c =$  probability of response in comparator arm; where  $p_c =$  probability of response in experimental arm.

Test for difference in proportion responders:

 $H_0: p_c - p_e = 0$ ; No difference in response probabilities

H1:  $p_c - p_e \neq 0$ ; difference in response probabilities

Table 4 illustrates the minimum detectable differences in the probability of responding (e.g., attaining seroconversion or  $NF_{50} \ge 0.56$  [seroprotection]) between participants who receive AV7909 as the lyophilized formulation or liquid formulation using a two-sided likelihood ratio test with 80% power and alpha = 0.05. It is assumed that up to 10% of subjects (N=2) will be excluded from the per-protocol analysis in each group. Seroconversion rates of 10% to 60% are considered.

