#### 9.3.1. Solicited Events and Symptoms

Systemic solicited adverse events were collected pre-vaccination, and systemic and local solicited adverse events were collected 30 minutes post-vaccination and then daily for 7 days after each vaccination and graded on a scale of 0 (absent), 1 (mild), 2 (moderate) and 3 (severe). Systemic events include fever, feverishness, fatigue, malaise, myalgia, arthralgia, headache, and nausea, with grading scales as defined in Table 8; the quantitative grading scale for fever is included in Table 9. Injection site events include pain, tenderness, pruritus, ecchymosis, erythema/redness, and edema/induration with grading scales as defined in Table 6. Ecchymosis, erythema/redness, and edema/induration are measured by both functional and measurement grading scales as defined in Table 7.

The number and percentage of subjects reporting at least one solicited adverse event will be summarized for each solicited adverse event, any systemic symptom, any local symptom, and any symptoms. Corresponding 95% CIs will be calculated using Clopper-Pearson methodology from a binomial distribution (SAS Proc Freq with a binomial option). Solicited events occurring post first vaccination will be presented in Table 35, post second vaccination in Table 36, and post any vaccination in Table 37. Summaries of solicited events following any vaccination will be stratified by sex in Table 38 and stratified by age category in Table 39.

For each systemic and local event, any systemic event, any local event, and any solicited event, the maximum severity over 7 days after each vaccination will be summarized for the safety population. The number and percentage of subjects reporting each event will be summarized by the maximum severity and study arm, separately for each vaccination and over all vaccinations (Table 40, Table 41 and Table 42).

The number of subjects reporting a solicited adverse event will be summarized for each day post vaccination for each vaccination and for all vaccinations combined both in tabular form (Table 43, Table 44, Table 45 and Table 46) and graphically in bar charts (Figure 15 and Figure 16). A comparison of the event rate for each study arm between vaccination 1 and vaccination 2 will be presented in Table 47.

Solicited adverse events by subject will be presented in Listing 10 and Listing 11.

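### The SAP sets out to compare lyophilized with liquid AV7909 on safety and reactogenicity, but its safety analyses contain no between-arm estimate

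*SAP*

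**What the plan says.** **Purpose.** SAP 2.1 lists safety, reactogenicity and "immunogenicity of the thermostable lyophilized formulation of AV7909 compared to the liquid formation of AV7909" as what the trial will assess. SAP 4.1 says that the safety, tolerability and immunogenicity of the two formulations "will be assessed and compared". The arms are randomised 1:1 within age and sex strata (SAP 4.4.3).

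**Protocol analysis.** Protocol 11.6.2 requires solicited events to be summarised by arm and names exact intervals as a technique. It then adds an option: "The proportion of participants reporting symptoms may be compared between treatment arms using Chi-square" or Fisher's exact test.

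**SAP analysis.**
- Tables 35-37, 40-42 and 48 give percentages with one-sample Clopper-Pearson intervals, by arm and for all subjects together.
- Tables 33, 38-39 and 43-46 give n and % only.
- The only comparison named in section 9.3.1 is dose 1 with dose 2 inside each arm: "A comparison of the event rate for each study arm between vaccination 1 and vaccination 2 will be presented in Table 47".
- No safety section or table shell contains a between-arm difference, ratio, interval or test.

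**Where a decision might have been recorded.** SAP section 1 presents the document as covering everything planned. Section 15 lists only the change in laboratory parameters. Section 13 sets a format for p-values, although no planned analysis produces one.

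**The concern.** Randomisation is what makes the lyophilized-versus-liquid contrast interpretable, and the SAP gives that contrast as the purpose of the trial. The tables then leave it without an estimate or a measure of uncertainty. The comparison that is planned, dose 1 against dose 2, is not randomised.

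Two errors of reading become more likely. A real difference in reactogenicity may be dismissed because the two arm-level intervals overlap. Similar percentages may be taken as evidence of similar tolerability, because nothing in the tables shows how large a difference the data still allow. If the difference is computed only after results are known, the method and the outcomes are also chosen at that point.

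**Working it through.** **Inputs.** Arm size from SAP section 5: "This study is planned to enroll a total of 40 subjects, with 20 subjects in each study arm". The 95% level follows the alpha in the same section: "As such, the type one error rate, alpha = 0.05, is not adjusted for multiple comparisons". The documents give no expected solicited-event rate by arm, so every count below is an assumption chosen for illustration.

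**1. The plan's own figure.** The Clopper-Pearson limits for x of n are the 0.025 quantile of Beta(x, n−x+1) and the 0.975 quantile of Beta(x+1, n−x). For 10/20 they are 27.2% to 72.8%; for 20/40, 33.8% to 66.2%. These match SAP Table 3 (27-73 and 34-66). That table describes the precision of a single percentage and says nothing about a difference.

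**2. Overlap can hide a clear difference.** Take 13/20 against 20/20.
- 13/20: 40.8% to 84.6%.
- 20/20: the lower limit is 0.025^(1/20) = 83.2%, the upper limit 100%.
- The intervals overlap between 83.2% and 84.6%.
- Fisher, two-sided: all 7 subjects without the event are in one arm, so p = 2 × C(20,7)/C(40,7) = 2 × 77,520/18,643,560 = 0.008.
- The Miettinen-Nurminen 95% interval for the 35-point difference is 15.9 to 57.0 points.

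The highest possible lower limit is 83.2%, and the upper limit at 13/20 already exceeds it. Once the lower arm reaches 13/20 (65%), the two intervals can therefore never separate. At 12/20 the upper limit is 80.9%, and they separate only from 20/20.

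**3. Identical rates leave much open.** Take 10/20 in each arm. The Miettinen-Nurminen interval is the set of d with (observed difference − d)² / V(d) ≤ 3.84. Here V(d) = [p1(1−p1)/20 + p2(1−p2)/20] × 40/39, with p1 and p2 fitted under p1 − p2 = d. By symmetry p1 = 0.5 + d/2 and p2 = 0.5 − d/2, so V(d) = (1 − d²)/39. Setting d² = 3.84(1 − d²)/39 gives d² = 3.84/42.84 = 0.0897, so d = 0.299. The interval is about −30 to +30 points. The planned tables would show 27-73% twice.

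**4. Starting from 10/20 in one arm.**

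| Other arm | Difference | 95% score interval (points) | Fisher p | One-sample intervals |
|---|---|---|---|---|
| 16/20 | 30 points | 0.1 to 55 | 0.096 | overlap |
| 17/20 | 35 points | 5.8 to 59 | 0.041 | overlap |
| 19/20 | 45 points | 19 to 67 | 0.003 | separate |

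**5. All 20-versus-20 tables, one direction.** Of 107 tables with Fisher p ≤ 0.05, 35 (33%) have overlapping one-sample intervals. Used as a rule, non-overlap has a type I error of about 0.1-0.2% at common rates of 30%, 50% and 80%, against 2.0-2.5% for Fisher. For 0.50 versus 0.89 its power is 33%, against 71% for Fisher.

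**The case against.** The strongest reply is that the SAP does what the protocol requires. The primary objectives are to assess, not to compare, the safety and tolerability of the formulations. The word comparative appears only in the secondary immunogenicity objective. Protocol 11.2 and SAP sections 5 and 6.8 disclaim formal hypothesis testing. On that reading, rates by arm with exact intervals suit a trial of 40 people. This explains the absence of p-values. It does not explain the absence of an estimated difference, given the wording of SAP 2.1 and 4.1, and a descriptive interval does not conflict with disclaiming tests.

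A reader might infer that the SAP breaks a protocol commitment. It does not: the protocol says the proportions may be compared, and what it offers is a test, not an estimate. What can fairly be said is that an option was left unused without comment.

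A reader might also infer that overlap of intervals is the only way left to compare the arms. It is not: n and N are tabulated side by side, so a difference can be computed, and neither document tells anyone to judge by overlap. Nor is every overlap misleading. At 10/20 versus 16/20 the score interval only just clears zero and Fisher's p is 0.096, so a test named in the protocol would agree with the overlap.

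The objection to volume also stands. Table 35 has 20 symptom rows. A difference for every row of Tables 35-37 would be 60 unadjusted intervals, of which about 60 × 0.05 = 3 might exclude zero by chance. That argues for a short list, not for none.

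**Conclusion.** The point holds as a modest gap between the stated purpose and the planned output. The SAP describes a comparison of safety and reactogenicity, and no safety table estimates it. Table 47 is a legitimate descriptive table, but it answers a different question.

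The gap has practical size at 20 per arm. A 35-point difference with Fisher p = 0.008 can sit behind overlapping intervals, and equal rates of 50% still allow a difference of about 30 points either way. Both figures rest on assumed counts. The first matters most if solicited-event rates are high, at 65% or more in the lower arm; the documents do not say whether they will be.

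The omission invalidates no planned summary, breaches no protocol requirement and does not call for hypothesis testing. It is worth correcting because the correction is cheap and answers the question the trial says it asks.

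**What to change.** Add to the SAP an unadjusted lyophilized-minus-liquid difference in percentage, with a 95% Miettinen-Nurminen interval, for:
- any injection-site, any systemic and any solicited event, in Tables 35, 36 and 37;
- moderate-or-worse any injection-site and any systemic events after any dose, as a derived row for each in Table 42, whose shell now lists each severity separately;
- at least one unsolicited adverse event, in Table 33.

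That is 3 × 3 + 2 + 1 = 12 intervals. Keep each table's existing denominator. Label the intervals as descriptive estimates, not tests, without multiplicity adjustment. State in the SAP whether the optional Chi-square or Fisher comparison will be used.

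**Cost.** SAP wording, one added column in four tables, and the derived rows with their difference in Table 42. No new data are needed. The intervals will be wide. With 12 at a nominal 5%, up to about 12 × 0.05 = 0.6 would be expected to exclude zero by chance if the formulations do not differ, which is why the label matters.

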#### 9.3.2. Unsolicited Adverse Events

When calculating the incidence of unsolicited AEs (i.e., on a per subject basis), each subject will only be counted once at the highest severity and/or relationship, and any repetitions of AEs within a subject will be ignored; the denominator will be the total number of subjects in the safety population. All AEs reported will be included in the summaries and analyses.

The number and percentage of subjects reporting at least one unsolicited AE will be summarized by MedDRA system organ class and preferred term. Denominators for percentages are the number of subjects who received the study vaccination. A 95% CI will be presented for the percentage of subjects reporting any unsolicited AE (serious or non-serious) for each MedDRA system organ class and preferred term.

The following summaries for unsolicited adverse events will be presented by MedDRA system organ class, preferred term, vaccination, and study arm:

• Subject incidence and total frequency of adverse events over time with 95% CI (Table 48).

- Incidence of AEs by severity and relationship to study product (Table 49 and Table 50).
- Subject listing of non-serious adverse events of moderate or greater severity (Table 52).
- Bar charts displaying total frequency and incidence of AEs by severity, MedDRA system organ class, and study arm (Figure 17 and Figure 18).
- Bar charts displaying total frequency and incidence of AEs by relationship to study product, MedDRA system organ class, and study arm (Figure 19 and Figure 20).

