### 3.2. Endpoints

#### 3.2.1. Primary

Safety:

- Occurrence of all SAEs through approximately 12 months following receipt of the second study vaccination (approximately Day 380).
- Occurrence of abnormal clinical safety laboratory AEs at approximately Day 29.
- Occurrence of all protocol specified AESIs (i.e., PIMMCs) and MAAEs, from the time of the first study vaccination through approximately 12 months following the second vaccination (approximately Day 380).
- Occurrence of unsolicited non-serious adverse events from the time of the first study vaccination through approximately Day 64.

Tolerability:

• Occurrence of solicited injection site and systemic reactogenicity events in the week after each study vaccination (Days 1 through 8 and Days 15 through 22, inclusive).

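### SAP Tables 49 and 50 do not restrict the unsolicited AE summary to non-serious events through about Day 64, so no planned table gives that primary outcome as defined

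*SAP*

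**What the plan says.** SAP 3.2.1, matching Protocol Table 1, lists as a primary safety outcome: "Occurrence of unsolicited non-serious adverse events from the time of the first study vaccination through approximately Day 64". It is one of five primary outcomes (four safety, one tolerability).

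Protocol 11.6.2 gives three separate instructions on unsolicited events:
- For the non-serious set: "Non-serious unsolicited AEs will be summarized as number and percentage of participants reporting at least one event" by preferred term and system organ class, "cross tabulated by severity and relationship to study product".
- The numbers of SAEs, medically attended AEs (MAAEs) and AEs of special interest (AESIs) "are likely to be small in this trial and will be reported by detailed listings".
- For AEs generally, "exact 95% confidence intervals of AEs in aggregate and by MedDRA® categories will be computed".

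SAP 9.3.2 states: "All AEs reported will be included in the summaries and analyses". It places the 95% confidence interval on the "percentage of subjects reporting any unsolicited AE (serious or non-serious) for each MedDRA system organ class and preferred term", which Table 48 displays. It assigns the breakdown by severity and relationship to Tables 49 and 50. The shells of those two tables mention neither seriousness nor an onset limit in title, columns or notes. SAP section 15, on changes to the planned analyses, mentions only the laboratory parameters that were dropped.

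**The concern.** The protocol separates the two sets: non-serious unsolicited AEs are tabulated, while SAEs, MAAEs and AESIs are listed. The SAP tables that carry the protocol's cross-tabulation merge them. The omission does not look like shorthand, because SAP 9.3.2 does specify non-serious events where it means them, for Table 52.

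At stake is whether a reader of the study report can find this primary outcome as it was defined. If an SAE or a late MAAE or AESI occurs, the printed figures may describe a different set of events over a longer period, under a title that does not say so.

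**Working it through.** There is no planned figure to reproduce, so the check sets the definition against each display and then sizes the possible difference.

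**1. Does any display meet the definition?** It needs unsolicited events only, non-serious events only, onset through about Day 64, and a count with percentage.

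| SAP display | Unsolicited only | Non-serious only | Day 64 limit | Count and % |
|---|---|---|---|---|
| Table 33, unsolicited AE row | yes | no | no | yes |
| Table 34, non-serious block | no | yes | no | yes |
| Table 48 | yes | no | no | yes, with CI |
| Tables 49, 50 | yes | no | no | yes |
| Table 52 | yes | yes | no | no; a listing of moderate or severe events |
| Listing 12 | yes | no, but SAE flag shown | no, but days post dose shown | no |

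None meets all four. SAP 9.3.2 also speaks of summaries by vaccination and, for Table 48, over time, but the shells of Tables 48 to 50 have no matching columns from which a Day 64 figure could be read.

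**2. Can Table 33 be used by subtraction?** No. Suppose it shows 7 participants with any unsolicited AE and 1 with an SAE. The number with a non-serious AE is 6 if that participant had nothing else and 7 if they also had a non-serious AE.

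**3. Does Table 34's threshold drop terms?** At 20 per arm, 1/20 = 5%, which meets the 5% threshold, so nothing is lost. With 21 in an arm (Protocol 5.2.5 permits replacement), 1/21 = 4.8%, and a term seen in one participant of that arm alone would not appear. The larger limits are that the block covers AEs in general and has no Day 64 cut.

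**4. Which events can separate the tabulated set from the defined set?** Ordinary non-serious unsolicited AEs are collected only to the Day 64 visit (SAP Table 1, note 17). Two kinds of event remain:
- SAEs, collected to about Day 380 (SAP 4.5.2). Their inclusion follows directly from the all-AEs rule.
- Non-serious MAAEs and AESIs with onset after Day 64, also collected to about Day 380. Protocol 9.2.1 makes an MAAE an unsolicited AE that led to unscheduled care. SAP 9.4 lists MAAEs and AESIs in Table 53, but nothing excludes them from Tables 49 and 50. Their entry is an inference.

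**5. Effect on any-event incidence.** Let a be the participants with at least one qualifying event, and k those with none who have an SAE or a counted late MAAE or AESI. The defined figure is a/N, the tabulated figure is (a + k)/N, and the difference is k/N.
- N = 20, k = 1: 1/20 = 5 points. For example, 6/20 = 30% becomes 7/20 = 35%.
- N = 20, k = 2: 8/20 = 40%, a difference of 10 points.
- N = 40 (all-subjects column of Table 49), k = 1: 1/40 = 2.5 points.
- k = 0: the two agree.

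**6. Effect within severity and relationship cells.** SAP 9.3.2 counts each participant once, at the highest severity and/or relationship. Take a participant in an arm of 20 with a mild non-serious AE before Day 64 and a severe SAE later. Under the definition they sit in the mild cell; in the pooled table they sit in the severe cell. Mild falls by 5 points, severe rises by 5, and any-event incidence is unchanged.

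**The case against.** The strongest reply has four parts.

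- **The protocol itself plans pooled intervals.** This stands for Table 48. A reader might take the SAP's serious-or-non-serious wording as the error, but that wording governs the interval, which implements the protocol's sentence on AEs in aggregate. It does not cover Tables 49 and 50, because the protocol attaches the severity and relationship breakdown to the non-serious set.
- **Collection applies the Day 64 limit by itself.** This largely stands. A reader might infer that late non-serious AEs of every kind flow into the tables; the collection rules do not support that. Nor do the documents establish that late MAAEs and AESIs will be counted. The protocol sends them to listings, and the SAP is silent on excluding them from these tables.
- **Other outputs fill the gap.** In part. Table 34 separates serious from non-serious events, Table 51 lists SAEs, and Table 53 flags SAE, MAAE and AESI status with days post dose. In 40 people, an analyst could identify who was counted only through an SAE. That is reconstruction from listings, not a reported outcome.
- **The trial is descriptive and such events should be few.** This stands, and it limits the weight of the point.

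Two further inferences fail. The difference is not always upward: that holds for any-event incidence, not for cells counted at the highest grade (step 6). And SAP 6.1 does not oblige the SAP to attach an interval to this summary. It says how intervals for percentages are calculated, and the protocol's non-serious sentence asks only for a count and percentage.

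**Conclusion.** Wrong as written, of minor severity. Tables 49 and 50 do not implement the non-serious summary that Protocol 11.6.2 plans, and no other SAP table presents this primary outcome as defined. The pooling of SAEs is certain from the text; the entry of non-serious MAAEs and AESIs after Day 64 is possible but unstated. Table 48 is not an error.

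The size is k/20 per arm for any-event incidence, or 5 points per participant counted only through such an event, and zero if there are none. This assumes 20 vaccinated participants per arm and no particular event rate. The protocol's expectation of few such events makes a small effect likely. The harm is to the labelling and reporting of a primary outcome.

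**What to change.** In SAP 9.3.2, restrict Tables 49 and 50 to non-serious unsolicited AEs with onset from first vaccination through the Day 64 visit (shifted where the second vaccination is late). Alternatively, leave them pooled and add one table so restricted. Give count and percentage by arm, by system organ class and preferred term, crossed with severity and relationship; an exact interval is optional.

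Keep Table 48 as the pooled display. Footnote its collection windows (ordinary non-serious events to about Day 64; SAEs, MAAEs and AESIs to about Day 380) and state whether non-serious MAAEs and AESIs after Day 64 are counted in it.

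The cost is a seriousness and onset filter, a footnote and at most one extra table. Listing 12 already carries the SAE flag and days post dose, so data collection does not change.
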